### Rescue Medication

The decision to medicate a participant will depend on if the therapists and study investigator determine the safety of the patient and others can be maintained without medical intervention. The final decision will be made by the study investigator.

- Benzodiazepine anxiolytics
  - The preferred pharmacological intervention of choice in case of acute psychological distress (e.g. medications such as lorazepam or alprazolam that have a rapid onset, a short time until peak plasma concentration, and a short duration of therapeutic action).
  - The oral route is preferable because IV injection procedures may further exacerbate the participant's anxiety.
- Antipsychotic medications (e.g. risperidone) should be available in the event that an adverse reaction escalates to unmanageable psychosis.
- Management of blood pressure:
  - Asymptomatic with blood pressure (BP) < 180/100
    - Reassure, ensure lights are dim or off, tilt head of bed 15 degrees up and continue to monitor
    - Increase blood pressure measurement frequency to q15min until BP has partly normalized (sBP = 100-159; dBP = 60-99)
  - Asymptomatic with BP <180/100 for >30 minutes
    - Administer captopril\* 12.5mg PO/SL x 1 with MD order

- Increase blood pressure measurement frequency to q15min until BP has partly normalized (sBP = 100-159; dBP = 60-99)
- Asymptomatic with BP persisting at >180/100 for >60 minutes post-dose, despite administering first captopril dose:
  - Consider potential transfer to ER – decision to be made by study investigator
  - Administer 2nd dose of captopril 12.5mg x 1 with MD order
- Management of severe treatment emergent hypertension:
  - Consider potential transfer to ER – decision to be made by study investigator
  - Administer captopril 25mg PO/SL x 1
  - Call 911 immediately for patients experiencing symptoms of a hypertensive crisis (e.g., chest pain, shortness of breath) or hypertensive encephalopathy (e.g., sudden severe headache, visual disturbances, seizures, diminished consciousness, or focal neurological deficit)
- Note: if there are contraindications to captopril, substitute for hydralazine 10mg PO

In case of development of acute anxiety or psychotic symptoms requiring pharmacological intervention, the participant will be managed under the care of the onsite psychiatrist. The participant may be discharged from the clinic when, in the opinion of the investigator, the condition has stabilized. The participant will be accompanied home. The participant is to notify the site when they have returned home safely. In the absence of receiving a phone call, site staff will directly contact the participant.

Information for how to manage subjects during difficult psychological states are detailed in the Yale Manual for Psilocybin-Assisted Therapy of Depression. All therapists will undergo training with the study investigator using this manual.

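### In the blood-pressure rescue rule (Section 5.6), the first two triggers read below 180/100 and the third above it, so the captopril trigger is wrong as written and severe hypertension is undefined

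*Protocol*

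**What the plan says.** Section 5.6, under Rescue Medication, sets out an escalating response to raised blood pressure in four parts.

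- Step 1, reassurance and checks every 15 minutes, applies to a participant who is "Asymptomatic with blood pressure (BP) < 180/100". The checks continue "until BP has partly normalized (sBP = 100-159; dBP = 60-99" mmHg).
- Step 2 applies to "Asymptomatic with BP <180/100 for >30 minutes" and gives captopril "12.5mg PO/SL x 1 with MD order", again with 15-minute checks.
- Step 3 applies to "Asymptomatic with BP persisting at >180/100 for >60 minutes post-dose, despite administering first captopril dose". It gives a second 12.5 mg and asks the investigator to consider transfer to an emergency room.
- The last part is headed "Management of severe treatment emergent hypertension". Its drug instruction is "Administer captopril 25mg PO/SL x 1", with transfer again to be considered. The symptoms listed beneath it (chest pain, sudden severe headache and so on) are the trigger for calling 911.

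On any decision to medicate, the section says: "The final decision will be made by the study investigator".

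**The concern.** The third step presupposes that pressure was already above 180/100 when the first captopril dose was given. The two steps leading to that dose, however, apply below 180/100. The signs therefore contradict each other within one short rule, and that rule decides when a drug is given.

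What is at stake is bedside safety. Read as written, the rule licenses an antihypertensive at ordinary pressures. It gives staff no numbered first action for the asymptomatic high reading that it appears to be written for. The final part, the only one left for such a reading, does not say what severe means and starts at the larger dose. Routine vital signs on dosing days are taken only every 1.5 hours (Section 6.1.2.1, Visits 3 and 4). The move to 15-minute checks is written only under the two triggers with the doubtful sign.

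**Working it through.** The protocol gives no figure to reproduce here, and no sample size or error rate is involved. The check sets the triggers side by side and runs readings through them.

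| Step | Trigger as written | Action |
|---|---|---|
| 1 | asymptomatic, below 180/100 | reassure, check every 15 minutes |
| 2 | asymptomatic, below 180/100 for more than 30 minutes | captopril 12.5 mg, 15-minute checks |
| 3 | asymptomatic, still above 180/100 despite the first captopril dose | second 12.5 mg, consider transfer |
| Severe | no value given | captopril 25 mg, consider transfer |

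**Literal reading**

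- *120/80 for 31 minutes.* 120 < 180, 80 < 100 and 31 > 30, so step 2 is met. This reading lies inside the partly normalized range (100-159 and 60-99). The same holds for every reading in that range, because 159 < 180 and 99 < 100.
- *190/110, asymptomatic.* 190 and 110 are not below 180 and 100, so steps 1 and 2 are not met. Step 3 requires an earlier captopril dose, which only step 2 provides. There is no numbered route to a first 12.5 mg, nor to 15-minute checks.
- *Exactly 180/100.* 180 < 180 is false and 180 > 180 is false; the same applies to 100. None of the three numbered steps is met.

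**Could steps 1 and 2 be meant for a moderate band?** Suppose an unstated floor just above the partly normalized range.

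- Systolic: 160 to 179, which is 179 - 160 + 1 = 20 whole-mmHg values.
- Diastolic: above 99 and below 100, which is 0 whole-mmHg values. A raised diastolic pressure could never bring these steps into play.
- Step 3 still speaks of pressure persisting above 180/100, which does not follow from a band that ends below it. A first reading above 180/100 still has no first step.

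**Does the protocol supply the missing threshold elsewhere?** No.

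- Section 4.4.2 excludes uncontrolled hypertension without giving a value.
- Section 3.2 and the Visit 3 and Visit 4 procedures only schedule measurements.
- Section 8.1 defines severe as a general adverse-event grade based on interference with normal activity, with no blood-pressure value.

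**Dose consequence.** If step 2 was meant for readings above 180/100, the first dose is 12.5 mg. If staff fall back on the severe part, it is 25 mg: 25 / 12.5 = 2 times as much.

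**With the sign reversed in steps 1 and 2,** the sequence is coherent: above 180/100, reassure and check; above it for more than 30 minutes, 12.5 mg; still above it despite that dose, a second 12.5 mg and consider transfer. The severe part would still lack a trigger.

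**The case against.** The strongest reply is that no clinician would follow the literal text. The section concerns rescue medication, and step 1's actions make sense only if pressure is raised. Each 12.5 mg dose needs a physician's order, and the investigator has the final decision. Section 5.4 has a licensed physician give the capsule and supervise, at least one therapist who is a clinician, and a psychiatrist on call. Uncontrolled hypertension is excluded at entry. All of this stands, and it makes harm from dosing at normal pressure unlikely. It does not correct the rule. The requirement for a physician's order is not written on the 25 mg line. Section 10.2 allows departures from the protocol without ethics board approval only to eliminate an immediate hazard, so staff who sensibly ignore the sign may still be outside the approved text.

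A second reply is that the severe part may be meant for symptomatic participants, since it alone omits the word asymptomatic. That is plausible, but the symptom list is tied to the 911 call and is not given as a definition. Sending an asymptomatic 190/110 to this part is therefore an inference, drawn because no other part could apply.

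A third is that a sign may have been altered when the PDF was read. This cannot be excluded from the text alone, but nothing points to it: the two less-than signs agree with each other, and the greater-than sign in the time limit of step 2 is intact.

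Finally, the counts of mmHg values measure no risk. That is fair; they show only that the moderate-band reading fails on the diastolic side.

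**Conclusion.** The concern holds. The trigger for the first captopril dose is wrong as written: it includes the whole partly normalized range and excludes the asymptomatic readings above 180/100 that the next step takes for granted. A reading of 180/100 meets none of the three numbered steps, and severe treatment-emergent hypertension has no stated criterion although it carries twice the first dose. The missing definition is secondary to the reversed sign.

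This rests on the signs having been read correctly from the PDF. The view that steps 1 and 2 were meant to read above 180/100 rests on the wording of step 3, so the investigators need to confirm it. No estimate, endpoint or sample size changes, and no number of affected participants is claimed. It should be fixed because it is a drug-trigger rule in a safety section, while the clinical oversight in place limits the likely harm.

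**What to change.** 1. Confirm the intended direction in steps 1 and 2 and correct it. Step 3 implies above 180/100. Writing at or above 180/100 in all three steps closes the gap at the boundary.
2. If the investigators also want action at systolic 160-179, write that as a separate step with both bounds and a diastolic range that is not empty. Changing the sign alone would leave that band without a step, although it lies above the protocol's own ceiling of 159 for partly normalized pressure.
3. Define severe treatment-emergent hypertension by a numeric threshold, by symptoms, or by both.
4. Reissue the instruction to dosing-room staff before dosing.

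The cost is one short protocol clarification or ethics board amendment and a corrected site instruction. Participants, data and sample size are unaffected.

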## 5.7 Packaging

The psilocybin will be provided by *Filament Health (Burnaby, British Columbia, Canada)*. The doses of psilocybin used in this study will be *10 mg and 25 mg*. The entire shipment for this trial will be sent in bulk (i.e. *20 capsules x 10 mg each, 20 capsules x 25 mg each*). Psilocybin capsules will be packaged individually in high-density polyethylene bottles (30cc). The dose for each participant will be stored in individual boxes labelled with the protocol number, trial name, lot number, unique box number, and a statement that the drug is for clinical use only. The IP will only be removed from the safe for one participant at a time on the day of their session. For a description of safety reporting, please see Section 8.3.1 of the protocol.

## **5.8 Blinding of Study Intervention**

Not applicable.

## **5.9 Receiving, Storage, Dispensing and Return**

### **5.9.1 Receipt of Study Intervention Supplies**

Upon receipt of the study intervention supplies, an inventory will be performed and a receipt log filled out and signed by the person accepting the shipment. Designated research staff/pharmacy must count and verify that the shipment contains all the items noted in the shipment inventory. Any damaged or unusable study intervention in a given shipment (active drug or comparator) will be documented in the clinical trial files.

### **5.9.2 Storage**

All IP will be kept in a locked area with limited access. The high-density polyethylene (HDPE) bottles of IP are to be stored as indicated in the investigators brochure. Bottles must be maintained at room temperature in a locked, secure location within research pharmacy. Deviations of storage temperature outside this required range should be documented and the study investigator should be notified immediately. Bottles of IP should not be frozen. If any component of the IP is damaged, the PI must be notified immediately. Any storage deviations that meet the criteria for reporting will be reported to the REB as a protocol deviation.

### **5.9.3 Dispensing of Study Intervention**

All participants will receive the same intervention. Each participant will be assigned 1 treatment bottle containing 1 capsule of either 10mg or 25mg of psilocybin. The IP will be dispensed and administered to the participants only by a licensed study physician. The study intervention will be administered orally, with water. Capsules should not be opened or chewed.

The investigator must keep an accurate accounting of the number of IP delivered to the site, administered to participants, and destroyed during and at the completion of the study. The IP is to be used in accordance with the protocol by participants. The study team, overseen by the PI, should maintain records that adequately document that the participants were administered the IP dose specified by the protocol.

Regular study intervention reconciliation will be performed to document study intervention assigned, consumed, and remaining. This reconciliation will be logged on an accountability log (i.e. drug accountability log), and signed and dated by delegated research and/or pharmacy staff.

#### **5.9.4 Return or Destruction of Study Intervention**

At the completion of the clinical trial, there will be a final reconciliation of the study intervention shipped, consumed and remaining. This reconciliation will be logged on an accountability form, and signed and dated by delegated research and/or pharmacy staff. Any discrepancies noted will be investigated, resolved, and documented prior to destruction of unused study intervention. Intervention destroyed on site will be documented in the clinical trial's files.

## **6.0 RESEARCH PROCEDURES**

### **6.1 Research Visits**

#### **6.1.1 Description of Measures**

##### **SCREENING MEASURES**

*Structured Clinical Interview for DSM-5 Clinician Version (SCID-5-CV).* The SCID-5-CV is a semi-structured diagnostic interview for ascertaining DSM-5 diagnoses. It will be administered by a trained study staff member.

*GRID Hamilton Depression Rating Scale-17 (GRID-HAMD-17).* The GRID-HAMD-17 is a standardized version of the Hamilton Depression Rating Scale, a clinician-rated measure of depression (J. B. W. Williams et al., 2008). In addition to the screening purpose, GRID-HAMD-17 will be used as an objective outcome measure (versus the subjective self-rated questionnaires as described as follows) for depression (Appendix B11).

*Autism Diagnostic Observation Schedule-2 (ADOS-2) Module 4.* The ADOS-2 is a semi-structured activity-based assessment for evaluation of autistic symptoms. The Module 4 targets intellectually and verbally capable adults with autism. It will be administered by study clinicians (Lord et al., 1989).

*Nine-item Form of Raven's Standard Progressive Matrices Test (RSPM).* The Raven's Standard Progressive Matrices instrument is a multiple-choice test used to assess mental ability associated with abstract reasoning, termed fluid intelligence. The standard form (RSPM) consists of 60 items, categorized into five sets of twelve matrices presented in black and white, and has been used as an indicator of general intelligence throughout the world. We will use a shortened set of items (nine items) that predicts the total score for the 60-item scale with good accuracy and fares well in clinical populations (Bilker et al., 2012). The reduction from 60 to 9 items represents an 85% reduction in the number of items to be administered. Nine-item Form of RSPM will be used to estimate the general intelligence, especially when a participant does not have a previous record of intelligence quotient derived from any other standardized intelligence scales (Appendix B16 and B17).

*For Baseline Autistic Features Associated with Depression:*

*Autism Quotient-12 (AQ-12)*. The widely used 50-item AQ tool, originally developed to identify autistic traits in adults of at least average intelligence, uses a 4-point Likert scale, ranging from ‘1’ (definitely agree) to ‘4’ (definitely disagree). Given the critiques of the AQ-50, including its length, factor structure and whether it is suitable to use as an autism severity measure, we will gather the 12 items identified by Lundqvist & Lindne (2017) as having utility to measure autism severity (Appendix B3).

*Adult Repetitive Behaviour Questionnaire-2 (RBQ-2A)*. The RBQ-2A is a 20-item self-administered tool scored on 4- and 3-point frequency or severity scales, with higher scores indicating greater severity. Following previous studies, the 4-point scaled items were collapsed to a 3-point scale, then a total sum score was used giving a possible score range of 20–60 (Barrett et al., 2018) (Appendix B14).

*Camouflaging autistic traits questionnaire (CAT-Q)* The Camouflaging Autistic Traits Questionnaire (CAT-Q) is a 25-item self-report questionnaire assessing the extent to which a person engages in social camouflaging behaviours, validated in autistic and non-autistic adults with equivalent factor structure between the groups. The CAT-Q captures three domains of social camouflaging: (1) “compensation” (behaviours used to compensate for autism-related difficulties in social situations); (2) “masking” (behaviours used to hide autistic characteristics or present a non-autistic personality to others); and (3) “assimilation” (behaviours used to fit in better with others and not “stand out” from the crowd). Participants rate each of the 25 questions on a seven-point Likert scale between “Strongly Agree” to “Strongly Disagree”. Responses are scored between 1 and 7, with higher scores for items which endorse presence of social camouflaging behaviour (Hull et al., 2019) (Appendix B6).

## SAFETY MEASURES

*Suicidal Behaviors Questionnaire – Autism Spectrum Conditions (SBQ-ASC)*. The SBQ-ASC is a self-report questionnaire used to measure suicidality in individuals with autism. It consists of 5 scored items: 1) lifetime experience of suicidal thoughts; 2) frequency of intense suicidal thoughts in the last 12 months; 3) perseverative intense suicidal thoughts; 4) likelihood of suicide attempts; 5) communication of future suicide intent & past suicide attempts to others. The SBQ-ASC also includes optional follow-up items which are not scored, based on responses to Item 5: for those who have attempted suicide, the follow-up items address presence of plans, impulsivity, and access to means. For those who have communicated suicide intent to others, the follow-up items address who was told about the participant’s suicidality. For those who have never communicated to others their suicidality, these follow-up items address the reason why it was never communicated. Furthermore, these follow-up items assess the lifetime experience of non-suicidal self-injurious behavior (Cassidy et al., 2021) (Appendix B18).

*UKU Side Effect Rating Scale*. The UKU side effect rating scale is a short and easy-to-use instrument that captures the core dimensions of side effects in patients using psychotropic medications. The UKU side effect rating scale is widely used in both research and in clinical settings (Lingjærde et al., 1987), and is delivered by interviewing and observing the patients and their caregivers. Herein, we will adopt the UKU side effect

rating scale specifically adjusted to adults with IDD, which consists of 35 items out of the original 48 items. This revised checklist seems more feasible to observe items that are concrete and objective than items based on the patients' subjective experiences (Tveter et al., 2014) (Appendix B20).

### Outcome Measures

#### For Secondary Endpoint:

*11 Dimensions of Altered State of Consciousness (11D-ASC).* The 11D-ASC is a 42-item scale. 11D-ASC consists of eleven dimensions: 1) experience of unity; 2) spiritual experience; 3) blissful state; 4) insightfulness; 5) disembodiment; 6) impaired control & cognition; 7) anxiety; 8) complex imagery; 9) elementary imagery; 10) audio-visual synesthesia; 11) changed meaning. It is well validated and widely used to characterize the subjective effects of psychedelic drugs. This self-rated scale appears as in a visual analogue scale with the upper anchor reading “much more than usual” and the bottom one reading “no more than usual” (Dittrich, 1998) (Studerus et al., 2010) and is scored by measuring the millimeters from the low end of the scale to the subject's mark (integers from 0–100) for each item. Participants will perform the 11D-ASC at the end of each dosing day when the subjective effects of psilocybin have subsided to a negligible level; however, ratings will be done with reference to the period when effects are most intense (Appendix B9).

#### For Exploratory Endpoint – Depression and Associated Symptoms:

*Clinical Global Impression Scale (CGI).* The CGI is a well-established research rating tool to provide a brief, stand-alone assessment of the clinician's view of the patient's global functioning prior to and after initiating a study medication. The CGI-Severity (CGI-S) asks the clinician one question: “Considering your total clinical experience with this particular population, how mentally ill is the patient at this time?” which is rated on the following seven-point scale: 1=normal, not at all ill; 2=borderline mentally ill; 3=mildly ill; 4=moderately ill; 5=markedly ill; 6=severely ill; 7=among the most extremely ill patients. This rating is based upon the average severity of observed and reported symptoms, behaviour, and function in the past seven days. The CGI-Improvement (CGI-I) is for the clinician to compare the patient's overall clinical condition to the baseline visit and is rated on a seven-point scale: “Compared to the patient's condition at admission to the project [prior to medication initiation], this patient's condition is: 1=very much improved since the initiation of treatment; 2=much improved; 3=minimally improved; 4=no change from baseline (the initiation of treatment); 5=minimally worse; 6= much worse; 7=very much worse since the initiation of treatment.” (Busner & Targum, 2007) (Appendix B8).

*Beck Depression Inventory II (BDI-II).* The BDI-II is a brief, self-report measure used to measure the severity of depression and related symptoms. It consists of 21 items, scored on a 4-point Likert scale ranging from 0 ('I do not feel sad') to 3 ('I am extremely sad'). Higher total scores indicate more severe depressive symptoms. It is a well-established tool that is used widely in clinical and research settings (Beck et al., 1996) and shows good psychometric properties in autistic adults (Z. J. Williams et al., 2021) ([https://asdmeasures.shinyapps.io/bdi\\_score/](https://asdmeasures.shinyapps.io/bdi_score/)) (Appendix B5).

*Snaith Hamilton Anhedonia Pleasure Scale (SHAPS)*. The SHAPS is a 14-item self-report scale that measures hedonic capacity. Participants are asked to rate themselves on a 4-point Likert scale from 0 ('strongly disagree') to 3 ('strongly agree'). It is both a reliable and valid measure that is frequently used in research and clinical settings (Snaith et al., 1995) (Appendix B19).

*Ruminative Responses Scale (RRS)-10*. The RRS-10 is a short form of RRS, a self-report rating tool used to describe responses to depressed mood (Treyner et al., 2003). It consists of 10 items and 3 factors (Brooding, Depression, Reflection), with each item being scored on a 4-point Likert scale from 1 ('never') to 4 ('always'), providing total scores ranging from 4 to 40 for ruminative symptoms. The psychometric properties of the RRS have been established in autistic adults (Z. J. Williams & McKenney, 2021) (Appendix B15).

*Anxiety Scale for Autism - Adults (ASA-A)*. The ASA-A is a self-report rating tool used to measure anxiety and related symptoms in autistic adults. It consists of 20 items, and a general anxiety factor alongside 3 group factors (Social Anxiety, Anxious Arousal, and Uncertainty). All items are scored on a 4-point Likert scale from 0 ('never') to 3 ('always'), with total scores ranging from 0 to 60. Higher scores indicate higher levels of anxiety (Rodgers et al., 2020) (Appendix B4).

*For Exploratory Endpoint – Theoretically Relevant Symptoms and Features:*

*General Alexithymia Factor Score (GAFS-8)*. The GAFS-8 is an 8-item scale derived from the Toronto Alexithymia Scale and is a self-report measure used to assess difficulty identifying and describing feelings. Items are scored on a 5-point Likert scale, ranging from 1 ('strongly disagree') to 5 ('strongly agree'). Total scores range from 20 to 100, with higher scores indicating more difficulty interpreting feelings and emotions (Z. J. Williams & Gotham, 2021) ([https://asdmeasures.shinyapps.io/TAS8\\_Score/](https://asdmeasures.shinyapps.io/TAS8_Score/)) (Appendix B10).

*Acceptance and Action Questionnaire-II (AAQ-II)*. AAQ II is a self-rated 7-item instrument to assess experiential avoidance and psychological inflexibility (Bond et al., 2011). Experiential avoidance is an attempt to avoid or neglect unpleasant thoughts, unpleasant feelings, bitter memories, uncomfortable physical sensations, and consequently leads to actions against one's values and causes long-term harm. Psychological inflexibility refers to rigid psychological reaction against one's values to avoid distress, uncomfortable feelings and thoughts and tendency to ignore the present moment. Both experiential avoidance and psychological inflexibility have been suggested as important elements in the etiology and the preservation of depression (Hayes et al., 2006) (Appendix B1).

*Autistic Burnout Survey Items (ABSI)*. ABSI is a 20-item self-rated assessment tool to quantify the experience of autistic burnout, comprising exhaustion, withdrawal, and cognitive overload, driven by stressors amplified in autistic people. The psychometric properties of this measure have been established in autistic adults (Arnold et al., 2023) (Appendix B2).

*Connor–Davidson Resilience Scale 10 (CD-RISC 10).* The CD-RISC 10 is a 10-item version of the CD-RISC, which is one of the most frequently used instruments to measure resilience (Campbell-Sills & Stein, 2007). Resilience describes the ability to 'bounce back' following difficult emotional experiences, and the flexibility to adapt to stressful and demanding situations. Lack of resilience may contribute to the development and maintenance of depression and anxiety in autism. The CD-RISC 10 has been validated as a measure of trait resilience in autistic adults (Hwang et al., 2020) (Appendix B7).

*Interoception Sensory Questionnaire-8 (ISQ-8).* The original form of the Interoception Sensory Questionnaire (ISQ) was developed to measure autistic adults' perception and interpretation of interoceptive sense (Fiene et al., 2018). Subsequently, a revised 8-item version (ISQ-8) using a condensed 5-point Likert scale was developed with good psychometric properties in autistic adults ([https://asdmeasures.shinyapps.io/ISQ\\_Score/](https://asdmeasures.shinyapps.io/ISQ_Score/)) (Suzman et al., 2021) (Appendix B13).

*Quality of Life.* We will gather the subjective experience of quality of life (QoL) using a self-rated measure, the WHOQOL-4 (Z. J. Williams & Gotham, 2021). The WHOQOL-4 includes four global QoL items from the content of the World Health Organization Quality of Life–Brief Version (WHOQOL-BREF). Collecting this QoL data could provide a reliable and valid estimate of QoL in autistic people while minimizing their burden given the 4 items in this measure vs. 49 items in the commonly adopted Autism Spectrum Quality of Life (ASQoL) (McConachie et al., 2018) (Appendix B21).

*Interpersonal needs questions—15 item (INQ-15).* The Interpersonal Needs Questionnaire (INQ-15) is a 15-item self-report questionnaire assessing 'thwarted belongingness' (e.g. 'These days, I often feel like an outsider in social gatherings') and 'perceived burdensomeness' (e.g. 'These days, I think I am a burden on society') (Van Orden et al., 2012). The INQ-15 has been used in previous research with autistic adults and those with high autistic traits (Cassidy et al., 2021) (Appendix B12).

*Custom-designed acceptability questionnaire.* We design two custom-designed questionnaires inquiring about the acceptability of all components of the main clinical trial and the optional dense sampling of brain MRI data, including recruitment, withdrawal rate, study visit attendance, protocol adherence and the time burden of completing questionnaires (Appendix B22 and B23).

*Cognitive Flexibility Inventory (CFI).* The CFI is a 20-item self-rated assessment tool to assess the core aspects of cognitive flexibility needed to challenge and replace maladaptive thoughts with more balanced & adaptive thinking. These core aspects include the ability to generate and accept alternative explanations for life occurrences & the agency an individual feels regarding their own life. Items are scored on a 7-point Likert scale with good psychometric properties (Dennis & Vander Wal, 2010). (Appendix B24).

